7.2. Observations and Measurements

Informed Consent

Potential subjects will be allowed to read a written informed consent form. The principal investigator, or designee, will explain all study procedures, risks, and alternative therapies to the subject. The subject will have an opportunity to have all questions answered. The appropriate parties will then sign and date the informed consent form, indicating willingness to participate in the study (see Section 7.5). A copy of the signed informed consent will be given to the subject.

All informed consent forms must be approved by Avid or designee, and by the appropriate Institutional Review Board (IRB) prior to use.

Medical History

The investigator or designee will obtain an updated history at the screening visit.

- Relevant demographic information
- Review of body systems
- Social history
- Medical and surgical history
- Concurrent medications

Whenever possible, the medical history will be confirmed by medical records.

Vital Signs

Vital signs (pulse rate, respiratory rate, supine blood pressure) will be taken at the following time points:

- Screening Flortetapi F 18 Imaging
 - Immediately prior to injection of flortetapi F 18
- ¹⁸F-AV-1451 Imaging Visit
 - Prior to the administration of ¹⁸F-AV-1451 Injection
 - After the completion of imaging, prior to discharge.

Height and Weight

At both imaging visits body weight will be measured, lightly clothed. Height will only be measured as part of the ¹⁸F-AV-1451 imaging visit.

Electrocardiogram

A resting ECG will be recorded at screening if a previous ECG performed within the last 12 months is not available for review.

Pregnancy Testing

- Serum beta hCG, qualitative: performed at screening for females of childbearing potential who are not surgically sterile. A serum pregnancy test may also be obtained prior to injection at the imaging visit if required by the local site.
- Urine beta hCG: performed at the ¹⁸F-AV-1451 imaging visit and florbetapir F 18 imaging visit (except as specified in section 7.1.1.1) prior to injection for females of childbearing potential (defined as pre-menopausal, less than 2 years post-menopausal or not surgically sterile).

MRI

Electronic copies of volumetric brain MRI scans obtained as part of the site’s companion protocol will be submitted to Avid, or designated imaging core lab. If one is not available for submission to Avid or designated imaging core lab, an MRI may be performed under this protocol if the subject is able to tolerate one. The MRI sequences and acquisition parameters will be described in a separate document.

Mini-Mental State Examination (MMSE)

The MMSE (Folstein et al., 1975) is a brief instrument used to assess cognitive function in elderly patients. The instrument is divided into 2 sections. The first section measures orientation, memory, and attention. The maximum score for the first section is 21. The second section tests the ability of the patient to name objects, follow verbal and written commands, write a sentence, and copy figures. The maximum score for the second section is 9. The range for the total MMSE score is 0 to 30.

Physician Visit

A physician must see the subject at screening to confirm that the subject is appropriate for participation in the trial. A physician or licensed/credentialed medical professional (that is, a PET technologist, imaging center nurse, or a regional equivalent) designated by the site principal investigator must see the subject at baseline, prior to drug administration and at study end, prior to discharge from the imaging sessions. At discharge, the physician or designee should review all safety data and briefly examine/query the subject regarding potential adverse events or other treatment issues.

7.3. Protocol for Image Collection

The sponsor will prepare and distribute imaging manuals for ¹⁸F-AV-1451 and florbetapir F 18 image acquisition parameters and transmission procedures prior to site initiation.

7.4. Good Clinical Practice and Monitoring

All clinical studies performed under the direction of Avid/CRO will be conducted in accordance with applicable regulatory requirements and International Conference on Harmonization (ICH) Good Clinical Practice (GCP) and Avid/CRO Standard Operating Procedures (SOP).

This includes:

1. IRB approval: An investigation will be initiated at a study site only after the IRB for that study site has given their written approval of the protocol and informed consent;
2. Informed Consent: Study procedures will not be initiated until the informed consent form is signed;
3. Recording and monitoring of adverse events as outlined in Section [7.7.3](#) including the notification of study site clinical investigators, local IRBs and the FDA regarding serious adverse event;
4. Avid RP’s obligation to monitor the participating center on a regular basis; and
5. The termination of a center or the trial if conditions apply, as outlined in Section [5.6](#).

7.5. Informed Consent and Subject Information

Potential subjects, or their legally authorized representative (as appropriate) will be allowed to read a written informed consent form. The principal investigator or designee will explain all study procedures, risks, and alternative therapies. The subject and legally authorized representative will have an opportunity to have all questions answered by a physician. The subject will then sign and date the informed consent form, indicating willingness to participate in the study.

Subjects with FTD are potentially a vulnerable population with compromised mental capacity. Investigators should take extra care to evaluate a patient’s ability to give consent. If the subject is capable of giving informed consent then the subject should sign on the consent line of the informed consent form. When applicable the legally authorized representative should sign as well, indicating that they have witnessed the subject’s consent, and further agree to participate as an informant.

If the subject is not capable of giving consent, consent may be given by a legally authorized representative, consistent with the requirements of the State where the subject resides and local IRB guidance. Subjects with the capacity to understand that they are engaging in a research study should affirm that they do not object to participating by signing on the Subject Assent line of the consent form. Subjects

lacking the capacity to assent and/or dissent will not be precluded from participation, but would not be required to sign the consent form.

All informed consent forms must be approved by Avid or designee, and by the appropriate Institutional Review Board (IRB). No study related procedures shall be performed prior to completion of the informed consent process, and signing of the consent form. A copy of the signed informed consent should be given to the patient for their records.

7.6. Documentation

¹⁸F-AV-1451 and florbetapir F 18 PET scans will be saved in an appropriate electronic format as specified in the imaging manuals. A copy of all scans, including the MRI scans will be saved at the site/imaging center and a copy of each will be forwarded to the sponsor or to the designated imaging core lab as described in the imaging manuals. All other data required by the protocol will be recorded in the eCRFs. All data in the eCRFs will be substantiated by “source documents,” which consist of the subject’s medical files, laboratory result sheets, ECG tracings, etc. All source documentation must be available to Avid, and its designees. Completed source documents and eCRFs may need to be made available and complete for an audit by the FDA, other international regulatory authorities, or Avid at any time. eCRFs and all other records must be filed in accordance with applicable laws and regulations (see Section 10.6).

7.7. Adverse Events (AE)

Avid’s standards for recording and reporting adverse events (AEs) are to be followed regardless of applicable regulatory requirements that may be less stringent. All AEs must be fully recorded on the adverse event eCRFs. Investigators will be instructed to report to Avid, or its designee, their assessment of the potential relatedness of each AE to study drug or protocol procedure via electronic data entry. If a patient’s treatment is discontinued as a result of an AE, study site personnel must clearly report to Avid, or its designee, via electronic data entry the circumstances and data leading to any such discontinuation of treatment. In cases where the investigator notices an unanticipated benefit to the patient, study site personnel should report “unexpected benefit” with the actual event term to Avid, or its designee (for example, the complete actual term would be “unexpected benefit- sleeping longer”).

Laboratory test abnormalities considered by the Investigator to be clinically relevant should be reported on the adverse event eCRFs. Signs and symptoms of each AE should be described in detail (e.g., start and stop dates/time, severity/intensity, relationship to study drug, action taken, and outcome).

Protocol ¹⁸F-AV-1451-A19: “¹⁸F-AV-1451 PET Imaging in Subjects with Frontotemporal Dementia”

Additionally, any clinically significant findings from laboratory evaluations, vital sign measurements, or other study procedures including those that result in a diagnosis should be reported as an AE to Avid, or its designee.

7.7.1. *Adverse Event Monitoring*

Each patient must be carefully monitored for adverse events. This includes clinical laboratory test variables. An assessment must be made of the severity/intensity and relationship to the administration of the study drug.

7.7.2. *Adverse Event Definitions*
Adverse Events

An adverse event is any undesirable experience occurring to a subject during a clinical trial, whether or not considered related to the study drug.

For reporting purposes, Avid will distinguish among pre-existing conditions, trial-emergent adverse events and treatment-emergent adverse events.

Pre-existing conditions (i.e., undesirable experiences, signs or symptoms that begin prior to the Screening Visit) will be recorded on the medical history eCRF pages. During the study, site personnel will record any change in the condition(s) and occurrence and nature of any AEs. Signs and symptoms that are believed to be due to the pre-existing condition(s) (started prior to dose of study medication) do not have to be recorded in the AEs section of the eCRF, unless there is an increasing in frequency and severity. Additionally, signs or symptoms or changes in pre-existing conditions that occur outside the trial defined adverse event reporting period (e.g., between each imaging visit will be recorded in medical history).

An adverse event is any untoward medical occurrence associated with the use of a drug in humans, whether or not considered drug related. For the purposes of this study, untoward medical occurrences will be considered associated with the use of ¹⁸F-AV-1451, and thus be reported as adverse events, if they occur within 48 hours after administration of ¹⁸F-AV-1451. Untoward medical occurrences will be considered associated with the use of Florbetapir F 18 injection, if they occur within 48 hours after Florbetapir F 18 injection administration. Adverse events associated with the use of ¹⁸F-AV-1451 or Florbetapir F 18 injection will be recorded as treatment emergent relative to the respective drug. Adverse experiences that occur after administration of either drug but outside the 48 hour reporting window will not be reported unless the investigator believes they are attributable to the drug.

Trial-emergent adverse events are undesirable experiences, signs or symptoms that begin, or worsen in intensity or frequency, after the informed consent, and

Protocol ¹⁸F-AV-1451-A19: “¹⁸F-AV-1451 PET Imaging in Subjects with Frontotemporal Dementia”

prior to administration of study drug at the imaging visit. In order to capture possible adverse effects of trial participation, trial-emergent AEs will also be reported during the baseline imaging period but not during the 48 hour windows following the administration of ¹⁸F-AV-1451 or Florbetapir. These will be recorded on the adverse event pages.

The end of study, for the purpose of adverse event reporting, is defined as 48 hours after the last study drug administration.

Serious Adverse Event (SAE)

A SAE is an AE that results in one of the following outcomes or constitutes one of the following events:

- Death;
- Initial or prolonged inpatient hospitalization (other than that required by protocol; “social hospitalization” or any hospitalization for non-medical reasons does not constitute a SAE);
- A life-threatening experience (that is, immediate risk of dying);
- Persistent or significant disability/incapacity;
- Congenital anomaly/birth defect;
- Considered significant by the investigator for any other reason.

Important medical events that may not result in death, be life-threatening, or require hospitalization may be considered serious adverse drug events when, based upon appropriate medical judgment, they may jeopardize the patient and may require medical or surgical intervention to prevent one of the outcomes listed in this definition.

Unexpected Adverse Event

An unexpected adverse event is an adverse event not previously reported or an adverse event that occurs with specificity, severity or frequency that is not consistent with the current IB.

Relationship to Study Drug

Investigators will be instructed to report their assessment of the potential relatedness of each adverse event to protocol procedure or study drug. The assessment of the relationship of an adverse event to the administration of the study drug is a clinical decision based on all available information at the time of the completion of the eCRF.

Intensity/Severity of an Adverse Event

Protocol ¹⁸F-AV-1451-A19: “¹⁸F-AV-1451 PET Imaging in Subjects with Frontotemporal Dementia”

In addition to assessing the relationship of the administration of the study drug to adverse events, an assessment is required, in order to determine the intensity (severity) of the event.

The following classifications should be used:

Mild:

A mild adverse event is an adverse event, usually transient in nature and generally not interfering with normal activities.

Moderate:

A moderate adverse event is an adverse event that is sufficiently discomforting to interfere with normal activities.

Severe:

A severe adverse event is an adverse event that incapacitates the subject and prevents normal activities. Note that a severe event is not necessarily a serious event; nor must a serious event necessarily be severe.

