6.6.2 Adverse Events

All adverse events (AEs) occurring after signing the informed consent are to be recorded on the AE pages of the case report form (CRF). Any pre-existing conditions (i.e., undesirable experiences, signs or symptoms that begin prior to the Screening Visit) will be recorded on the medical history eCRF pages. The investigator's verbatim term of AEs will be mapped to SOC and PT using the MedDRA v 21.1 or higher.

Adverse Events:

An AE is any undesirable experience occurring to a subject during a clinical trial, whether or not considered related to the study drug. In this study clinically relevant abnormal finding, as well as worsening of any pre-existing condition shall be recorded as an AE. AEs that occur after administration of either drug but outside 48 hour reporting window will not be reported unless those are attributed to the study drug.

Unexpected Adverse Events:

An unexpected adverse event is an adverse event not previously reported or an adverse event that occurs with specificity, severity or frequency that is not consistent with the current Investigator's Brochure (IB).

Serious Adverse Events (SAEs):

Serious AEs (SAEs) are events that result in one of the following outcomes or constitute one of the following events:

- Death
- Initial or prolonged hospitalization
- A life-threatening experience (that is, immediate risk of dying)
- Persistent or significant disability/incapacity
- Congenital anomaly/birth defect
- Considered significant by the investigator for any other reason

Important medical events that may not result in death, be life-threatening, or require hospitalization may be considered serious adverse drug events when, based upon appropriate medical judgment, they may jeopardize the patient and may require medical or surgical intervention to prevent one of the outcomes listed in this definition.

For the summarization of AEs by seriousness, events recorded with missing seriousness will be summarized as serious, following worst case principle.

Trial Emergent Adverse Events:

Trial Emergent AEs are defined as any AEs that occur or worsen (increase in intensity and/or frequency) after the informed consent, and prior to administration of Florbetapir F 18, or between the Florbetapir F 18 injection session and Flortaucipir F 18 injection session but outside the 48 hours window following administration of Florbetapir F 18 or Flortaucipir F 18.

Treatment Emergent Adverse Events (TEAEs):

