TEAEs are defined as any AEs that occur or worsen (increase in intensity and/or frequency) after administration of Flortaucipir F 18 or Florbetapir F 18 and until 48 hours post administration.

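### The protocol lets sites leave a pre-existing symptom off the AE page unless it worsens in both frequency and severity, but the SAP counts worsening in either, so the TEAE tables may miss some events

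*Protocol*

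**What the plan says.** **The exemption.** Protocol 7.7.2 sends conditions that began before screening to the medical-history pages. Symptoms that the investigator believes are due to such a condition "do not have to be recorded in the AEs section of the eCRF, unless there is an increasing in frequency and severity".

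**The protocol's other statements, also in 7.7.2.**
- On changes in pre-existing conditions: "site personnel will record any change in the condition(s) and occurrence and nature of any AEs". No page is named.
- Untoward occurrences count as associated with flortaucipir, "and thus be reported as adverse events, if they occur within 48 hours after administration of" that tracer. The association rule for florbetapir uses the same window. Neither mentions worsening.
- Trial-emergent events are undesirable experiences, "signs or symptoms that begin, or worsen in intensity or frequency, after the informed consent" and before dosing at the imaging visit. They exclude the 48 hours after each tracer. On where they go: "These will be recorded on the adverse event pages".

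**The SAP.** Section 6.6.2 covers trial-emergent events as "any AEs that occur or worsen (increase in intensity and/or frequency) after the informed consent" and outside the 48-hour windows. For the post-dose period, "TEAEs are defined as any AEs that occur or worsen (increase in intensity and/or frequency) after administration" of either tracer, up to 48 hours. The same section says that "worsening of any pre-existing condition shall be recorded as an AE". Section 8.10.2 restricts the AE summary tables to TEAEs unless otherwise specified. Section 8.7 puts medical history in a listing only.

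**The concern.** The test that decides whether a symptom must be entered is narrower than the test that decides whether it is counted. Suppose a subject has agitation at baseline, and within hours of injection it becomes severe but no more frequent. If the investigator attributes it to the underlying dementia, the exemption does not require an AE entry. Under the SAP the same event is a TEAE.

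Expanding the flortaucipir safety database is the study's secondary objective. Protocol 5.3.1 enrols only symptomatic patients, so every subject has pre-existing symptoms to which the exemption could apply. An omission can only lower the reported count, and permissive wording leaves room for sites to differ.

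**Working it through.** The documents give no figure to reproduce and no formula applies. The check is a comparison of the rules.

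**Step 1: the four possible courses of a symptom attributed to a pre-existing condition.**

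| Change after consent | AE entry required by the exemption sentence? | Meets the protocol's trial-emergent wording (outside the 48-hour windows)? | Meets the SAP wording for trial-emergent events or TEAEs? |
|---|---|---|---|
| None | No | No | No |
| More frequent only | No | Yes | Yes |
| More severe only | No | Yes | Yes |
| Both | Yes | Yes | Yes |

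The rules agree in the first and last rows. The conflict is confined to the two middle rows.

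**Step 2: outside the 48-hour windows.** Here the conflict lies within Protocol 7.7.2. The exemption releases the site from entering a one-dimension worsening. The trial-emergent definition includes that worsening and sends it to the AE pages. A further sentence in 7.7.2 sends changes between imaging visits to medical history, which adds to the uncertainty. In SAP 8.10.2 these events feed one line of the overview and one table.

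**Step 3: inside the 48-hour windows.** The trial-emergent definition does not apply here, so its *or* wording gives no help. The 48-hour rule covers untoward occurrences without saying what counts as a worsening. For symptoms of a pre-existing condition, the exemption is the only explicit test of worsening in the protocol. The either-dimension test for TEAEs stands in the SAP alone, so in this period the conflict is between protocol and SAP. This period feeds the TEAE tables.

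**Step 4: can the analysis make good an omission?** SAP 6.6.2 and 6.6.2.1 apply worst-case rules when seriousness, severity or relationship is missing. Those rules act on events already entered. A worsening noted only in medical history would appear in that listing and in no TEAE table. SAP 5.2 declares no change from the protocol's planned analyses, so the mismatch is not acknowledged.

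**Step 5: size.** The undercount depends on how often one-dimension worsening occurs and how often sites use the exemption. The documents give neither, so it cannot be computed.

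**The case against.** The strongest reply is that the exemption forbids nothing and that other text calls for entry. Protocol 7.7, 7.7.3 and 10.7 require all AEs to be recorded on the eCRF. Section 7.7.2 asks for any change in a pre-existing condition to be recorded, and its 48-hour rule carries no two-dimension test. The agitation example fits that rule as well as the exemption. Subjects are observed during imaging, queried at discharge, and telephoned no earlier than 48 hours after injection.

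Much of this stands. A reader might infer that one-dimension worsenings never reach the AE page. The documents do not support that: a careful site could enter every one. Nor need an unentered event be lost altogether, because it may survive in medical history or source notes.

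The reply does not remove the conflict. The requirement to record all AEs is general, whereas the exemption is a specific instruction on which symptoms need no AE entry, and a site can follow it in good faith. The instruction to record any change names no page. The SAP's sentence on worsening is not an instruction to sites. The SAP also cites a CRF dated 28 March 2018, well after the protocol of 5 May 2016.

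A reader might also infer that the symptoms of frontotemporal dementia are those most likely to be worsened by tracer or scan. Nothing in the documents establishes this. Differences between sites are likewise a possibility, not a finding, and the eCRF completion guidance is not among the documents.

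**Conclusion.** The wording conflict is certain and its consequence is possible. A worsening in one dimension only may be left off the AE page, or entered inconsistently, and the TEAE tables would then miss it. TEAE counts could be biased downward by an amount that the documents do not allow to be computed. This rests on some investigators attributing the symptom to the pre-existing condition and relying on the exemption.

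Two tempting figures do not measure the problem.
- **One pattern in three.** Of the three ways to worsen, the exemption requires entry of one. That counts logical categories, not events.
- **Four percentage points per missed subject.** This is 1/25 = 4.0%, which takes 25 as the denominator. Enrolment is up to 25, so it could be smaller. The safety population also includes anyone given florbetapir alone, so it could be larger; with 30 dosed (an assumption), 1/30 = 3.3%. Overall incidence falls only if the missed event was that subject's sole TEAE.

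The point deserves correction because the remedy is small and completeness of the safety data serves a stated objective. It does not affect the imaging analyses.

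**What to change.** In Protocol 7.7.2, change the exemption so that an increase in frequency *or* severity triggers an AE entry. This matches the trial-emergent definition in that section and SAP 6.6.2. Repeat the rule in the eCRF completion guidance.

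If data are already collected, review the medical-history entries and source notes for each 48-hour post-dose window before database lock. Look for symptoms that worsened in one dimension only, and query the site where one is found. State any remaining limitation in the SAP and in the study report.

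The protocol change is one word plus a guidance note. The downside is slightly more AE entries and a possibly less favourable AE rate. A retrospective review adds site queries for a study of up to 25 enrolled subjects.

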7.7.4. Reporting of Serious Adverse Events

Study site personnel must alert Eli Lilly, or its designee, of any SAE within 24 hours of their awareness of the event via a sponsor-approved method. Alerts issued via telephone are to be immediately followed with official notification on study-specific SAE forms.

Serious adverse events occurring after a subject receives a dose of study drug will be collected in the eCRF as Adverse Events until 48 hours after the dosing of the study drug, regardless of the investigator's opinion of causation. Thereafter, SAEs are not required to be reported in the eCRF as Adverse

Events unless the investigator feels the events were related to either investigational product or drug delivery system, or a protocol procedure. If the investigator does not feel the event was related to the investigational product or drug delivery system or protocol procedure, then the event should be recorded in the eCRF as Medical History for the subject. Regardless of the investigator’s assessment of relatedness or timing, all SAEs that occur after the subject receives the investigational product should be submitted to Lilly GPS for processing to determine applicability of any expedited reporting requirements..

If a patient experiences a SAE after signing informed consent, but prior to receiving study drug, the event will NOT be reported unless the investigator feels the event may have been caused by a protocol procedure. Previously planned (prior to signing the ICF) surgeries should not be reported as SAEs unless the underlying medical condition has worsened during the course of the study.

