10.7. Adverse Events

All adverse events encountered during the clinical trial must be documented on the eCRF, whether or not considered drug-related.

Eli Lilly and Company must be notified immediately (as soon as possible, and in all cases within 24 hours) of a drug experience, condition, development, or event, which is considered serious. Eli Lilly and Company must be notified immediately of any findings with the use of the drug that may suggest significant hazards, contraindications, adverse drug reactions (ADRs) and precautions pertinent to the safety of the drug. The investigator will be requested to complete a separate report form in addition to the information on the eCRF. See section [7.7.4](#) for reporting serious adverse events

If a SAE is determined to be unexpected (not previously reported or described by Avid), and study drug-related, Eli Lilly and Co. will notify the investigator in writing. The investigator should forward this notification to the IRB within 24 hours of receipt.

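### Events between the two tracer injections, more than 48 hours after florbetapir, fall under three incompatible recording rules, so the trial-emergent adverse event table may be incomplete and may differ between sites

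*Protocol*

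**What the plan says.** **Protocol 7.7.2** contains three instructions that reach the interval between the two imaging visits:

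- Medical history: signs, symptoms or changes in pre-existing conditions "outside the trial defined adverse event reporting period (e.g., between each imaging visit will be recorded in medical history".
- Not reported: experiences after either drug but "outside the 48 hour reporting window will not be reported unless the investigator believes they are attributable to the drug".
- AE page: "trial-emergent AEs will also be reported during the baseline imaging period but not during the 48 hour windows". The section adds: "These will be recorded on the adverse event pages".

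**Protocol 7.7.4** says that, once 48 hours have passed since dosing, an SAE judged unrelated to the product, its delivery system or a procedure is entered in the eCRF as medical history. Its last paragraph turns to SAEs in subjects who have consented and are not yet dosed: "prior to receiving study drug, the event will NOT be reported unless the investigator feels the event may have been caused". The exception is for events that a trial procedure may have brought about.

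**Protocol 10.7** gives the opposite general rule: "All adverse events encountered during the clinical trial must be documented on the eCRF, whether or not considered drug-related". Protocol 7.7.3 likewise puts every adverse event on the AE eCRF, with serious ones also on the SAE form.

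**SAP 6.6.2** opens with "All adverse events (AEs) occurring after signing the informed consent are to be recorded on the AE pages". It then says that events outside the 48-hour window are not reported unless attributed to the study drug. It goes on to define events between the two injection sessions and outside 48 hours as trial-emergent.

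**SAP 8.10.2** plans a trial-emergent line in the overall summary and a trial-emergent table by SOC and PT. SAP 8.7 presents medical history as a listing only.

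**The concern.** Take a subject with a new event 5 days after florbetapir, before flortaucipir is given. One site enters it in medical history, a second leaves it out because the investigator does not blame the drug, and a third enters it on the AE page. Each can point to a sentence in Protocol 7.7.2. Only the third event reaches the trial-emergent table. The first appears in a listing, and the second may leave no eCRF record.

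Two things are at stake. The counts may not be comparable across the approximately 3 centers that SAP 7.5 pools. Inclusion may also turn on attribution, although Protocol 7.7.2 says trial-emergent events are collected to capture possible effects of taking part in the trial. For serious events the SAP calls a between-session event trial-emergent, while Protocol 7.7.4 can send it to medical history.

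**Working it through.** The plan gives no event rate, power or other figure on this point, so there is nothing to reproduce. The check is to set the rules side by side and then bound how much time and how many subjects they could touch.

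**Step 1. Which rule applies when**

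| Event | Medical history | Not reported | AE page |
|---|---|---|---|
| New, non-serious, after consent and before the first injection | no | no | yes (7.7.2; SAP 6.6.2) |
| Within 48 h of an injection | no | no | yes, treatment-emergent |
| Non-serious, between injections, more than 48 h after florbetapir | yes (7.7.2) | yes, unless attributed to the drug (7.7.2; SAP 6.6.2) | yes, trial-emergent (7.7.2; SAP 6.6.2) |
| Serious, unrelated, between injections, more than 48 h after florbetapir | yes (7.7.2, 7.7.4) | yes, unless attributed to the drug (7.7.2; SAP 6.6.2) | yes (7.7.3; SAP 6.6.2) |
| Serious, after consent and before study drug | no | ambiguous (7.7.4, with a procedure exception) | yes (7.7.3, 10.7; SAP 6.6.2) |

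The third and fourth rows contain the conflict, and the fifth is an ambiguity. Protocol 7.7.2 ends adverse event reporting 48 hours after the last study drug, so the time between visits lies inside the reporting period. The medical-history sentence nevertheless uses it as its example of time outside.

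**Step 2. How much time is disputed**

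Inputs: 48-hour window (Protocol 7.7.2); minimum 16 hours between scans (7.1.2); screening preferably within 60 days before flortaucipir (7.1.1), which is a preference and not a limit; a prior amyloid scan within 3 years may replace florbetapir (7.1.1.1).

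Disputed time = max(0, gap between injections − 48 h).

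- 16 h gap: 0
- 48 h gap: 0
- 7-day gap: 7 − 2 = 5 days (71% of the gap)
- 30-day gap: 30 − 2 = 28 days (93%)
- 60-day gap: 60 − 2 = 58 days (97%)
- Prior amyloid scan, no florbetapir injection: 0

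**Step 3. How many subjects could be touched**

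Let p be the chance that a subject has at least one event in the disputed time. The documents do not give p, so the values below are assumptions, with subjects taken as independent. Expected subjects = n × p, and the chance of at least one = 1 − (1 − p)^n. The first case takes n = 25 (Protocol 8.1.1 enrols up to 25). The second assumes that only 10 subjects have an injection gap above 48 hours.

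| p | Expected, n = 25 | At least one, n = 25 | Expected, n = 10 | At least one, n = 10 |
|---|---|---|---|---|
| 1% | 0.25 | 22% | 0.1 | 10% |
| 5% | 1.25 | 72% | 0.5 | 40% |
| 10% | 2.5 | 93% | 1.0 | 65% |
| 20% | 5.0 | 99.6% | 2.0 | 89% |

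These are chances that the rules are put to the test, not chances that an event is lost.

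**Related gap.** The SAP's trial-emergent definition is tied to florbetapir. It does not say how to class an event after consent and before flortaucipir in a subject who had no florbetapir injection.

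**The case against.** The strongest reply is that the text can be partly harmonised. The not-reported sentence sits in a paragraph on events associated with each drug, and the next paragraph adds that trial-emergent events are reported as well. The medical-history sentence sits in a paragraph on pre-existing conditions. Protocol 7.7.3 and 10.7 and the opening of SAP 6.6.2 all call for complete recording, and a site that follows them loses nothing. The CRF cited in SAP section 2 is not among the documents, so actual capture is unknown.

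This reply stands against certainty, but it does not remove the conflict. The not-reported sentence covers events after either drug, which takes in the time after florbetapir. SAP 6.6.2 repeats it beside a definition that includes the same events. Even if the medical-history sentence is limited to pre-existing conditions, a worsened condition is trial-emergent by definition.

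A reader might infer four stronger points, which the documents do not support:

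- *The table will be undercounted.* The general rules direct full recording, and the disputed time can be zero.
- *All events before an injection are affected.* New non-serious events before the first injection have one clear rule, the AE page.
- *Serious pre-dose events are omitted.* The last paragraph of 7.7.4 has a procedure exception and sits in the section on SAE reporting. It can be read as covering notification only, and 10.7 refers to 7.7.4 for SAE reporting. It is ambiguous, not a shown omission.
- *About 97% of events are at risk.* That figure is a share of calendar time at an assumed 60-day gap, not a share of events.

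It is also fair to say that the secondary objective concerns the flortaucipir safety database, and these events occur before flortaucipir is given.

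**Conclusion.** The point holds for one interval: between the two injections and more than 48 hours after florbetapir. There, Protocol 7.7.2 gives three incompatible instructions, SAP 6.6.2 carries over the clash between not reporting and trial-emergent, and Protocol 7.7.4 adds a medical-history route for unrelated SAEs. For SAEs before study drug, the wording is at least ambiguous.

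The consequence is that one overview line and one SOC/PT table may be incomplete, may differ between sites and may depend on attribution. How far depends on the injection gaps and the event rate, neither of which the documents fix. The 0 to 48 hour treatment-emergent tables are largely unaffected, because events in those windows go to the AE page, and so are the imaging analyses. This is an internal inconsistency worth correcting; it does not threaten the primary objective.

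**What to change.** Reconcile Protocol 7.7.2 and 7.7.4 and SAP 6.6.2 to one recording rule per interval:

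1. From consent to 48 hours after the last tracer, every new or worsened event, serious or not, goes on the AE eCRF page and is classed by timing as trial-emergent or treatment-emergent.
2. For that period, remove the medical-history and not-reported wording from 7.7.2 and SAP 6.6.2, and the medical-history route for unrelated SAEs from 7.7.4.
3. State that the last paragraph of 7.7.4 concerns SAE notification only and does not govern what goes on the AE page.
4. In the SAP, name the source pages for the trial-emergent table, and say how events before flortaucipir are classed in subjects without a florbetapir injection.

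If site recording can no longer change, the SAP can bring into the trial-emergent table those medical-history entries with onset after consent, before flortaucipir and outside the florbetapir 48-hour window. This recovers misdirected events where onset dates were recorded, but not events that were never written down.

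The cost is a wording change in both documents, a note to sites and a few more AE entries.
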